11 EFFICACY ASSESSMENTS

11.1 Oral Mucositis (OM) Assessments

Mucositis assessments will be completed at the screening visit, day 1 of pretreatment prior to administration of RRx-001, twice weekly (no less than 48 hours apart) within each 5-day radiation week during the combination treatment phase, at the end of the combination treatment phase (last day of radiation) and the same day each week (± 1 day) during the Mucositis Observation Follow-up until resolution of ulcerative mucositis occurs (WHO grade 0 or 1).

Oral mucositis will be assessed by a trained evaluator using a standard oral mucositis assessment instrument. If a patient withdraws prior to the end of the combination treatment phase, an oral assessment must be completed on the day of withdrawal, and it is suggested that patients be assessed weekly until resolution of ulcerative mucositis occurs (WHO grade 0 or 1). Patients will be instructed not to discuss their treatment regimens with the assessor. Additionally, the assessor will be provided training to assure uniform interactions with patients to limit bias in the assessment.

Specific training and instructions are required for all individuals who perform mucositis assessments. Such training will be provided by the sponsor or its designee. Site study staff

designated as oral evaluators must be licensed professionals and properly delegated such tasks (on DOA log). Oral evaluators will conduct all assessments using a standardized and consistent method. To reduce inter-observer variability, as few oral evaluators as possible should be involved in the assessments of an individual patient. Ideally, the same assessor will evaluate a single patient throughout the combination treatment and mucositis observation follow-up. All efforts to maintain uniformity should be used.

The study's efficacy endpoints will be based on WHO mucositis criteria. Since patients' ability to eat is a component of the WHO scale, standardization of the assessment of food intake and, particularly, the definition of solids, liquids and "nothing by mouth" is critical.

- A normal solid diet is defined as firm, shaped food that does not flow or conform to the shape of its container and requires chewing. Examples include rice, meat including fish, poultry, bread, rolls, toast, salad, cereal.
- A modified soft solid diet consists of foods that do not conform to the shape of its container, still require minimal chewing, but are less dense than standard solids. Examples include eggs, pasta, fruit or soup.
- For the purposes of the clinical trial mucositis assessment, liquids are defined as foods that take the shape of their container and which don't require chewing. In addition to things we typically think of as pure liquids like juice, milk shakes, smoothies or frappes, also heavily pureed foods, yogurt, oatmeal and jello fall into this category.
- The "nothing by mouth" category is appropriate for patients who can't eat or swallow EXCEPT for medication. Please note that sips of water used to help aid in swallowing medication still constitute a "nothing by mouth" selection. This would also be the best option for patients who require the assistance of a feeding tube.

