**Appendix C. Oral Mucositis WHO Grading System**

Grade	Description
0 (none)	None
I (mild)	Oral soreness, erythema
II (moderate)	Oral erythema, ulcers, solid diet tolerated
III (severe)	Oral ulcers, liquid diet only
IV (life-threatening)	Oral alimentation impossible

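### Section 11.1 lists soup as a soft solid, but smooth soup meets the section's own definition of a liquid, so some patients with ulcers can be scored WHO grade II or grade III

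*Combined protocol and SAP*

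**What the plan says.** Section 11.1 bases the efficacy endpoints on the WHO criteria and, because eating is part of that scale, calls "standardization of the assessment of food intake" critical, naming in particular the definitions of solids, liquids and nothing by mouth. Three of its definitions matter here:

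- Soft solids: "A modified soft solid diet consists of foods that do not conform to the shape of its container, still require minimal chewing". The examples follow: "Examples include eggs, pasta, fruit or soup".
- Liquids: "liquids are defined as foods that take the shape of their container and which don't require chewing".
- Liquids, further examples: "also heavily pureed foods, yogurt, oatmeal and jello fall into this category".

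Appendix C describes grade II as "Oral erythema, ulcers, solid diet tolerated" and grade III as "Oral ulcers, liquid diet only". It has no entry for a modified soft solid diet.

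Section 13.2 defines SOM as grade 3 or 4. One such score makes a patient an incident case. Duration runs from the first such score to the first grade 2 or lower after the last such score. Time to onset runs from the start of chemotherapy to the first such score.

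**The concern.** The example and the definitions in Section 11.1 disagree about a food that a patient with mouth ulcers might plausibly live on. The disagreement falls on the boundary between a solid and a liquid-only diet. In a patient with ulcers, that boundary separates grade II from grade III, and so separates not severe from severe. SOM incidence, time to onset and duration all use this cut.

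If assessors resolve the conflict differently, patients in the same condition receive different outcomes. Inconsistency unrelated to treatment adds misclassification and tends to blur a real difference. Inconsistency related to treatment would bias the comparison, and administration of RRx-001 is not blinded.

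**Working it through.** The plan gives no figure on this point to reproduce, so the check is a side-by-side reading followed by short arithmetic.

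**Step 1. Apply the two definitions.** A soft solid must keep its own shape and need a little chewing. A liquid must take the container's shape and need no chewing. The physical properties of soup below are ordinary knowledge, not taken from the documents.

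| Food | Takes container's shape | Needs chewing | By definition | By listed example |
|---|---|---|---|---|
| Clear, smooth or pureed soup | yes | no | liquid | soft solid |
| Soup with pieces that need chewing | yes (the broth) | yes (the pieces) | neither in full | soft solid |
| Oatmeal, yogurt | not needed, listed by name | not needed | liquid | liquid |

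The conflict is complete for smooth soup. It also reverses the order of thickness: a patient living on oatmeal counts as liquid-only, while one living on thinner soup counts as eating soft solids.

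**Step 2. Carry this to Appendix C**, for a patient with ulcers whose most solid food is smooth soup.

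- By the example: soft solid, hence a tolerated solid diet, hence grade II, not SOM. The middle link is inferred from the category's name; the protocol does not write it down.
- By the definition: liquid diet only, hence grade III, SOM.

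**Step 3. Which endpoints move.** SOM incidence, onset and duration can change. Incidence and duration of ulcerative mucositis (grades 2 to 4) cannot, because both readings give at least grade II. Patient-reported pain does not use the WHO grade.

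**Step 4. Size per affected patient.** Inputs are 10 patients per group (Section 13.1) and the visit spacing in Section 11.1.

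- Incidence: 1/10 = 10 percentage points on the arm. This needs every grade 3 or 4 score of that patient to turn on soup, because one other severe score keeps the patient a case.
- Duration during radiotherapy: two visits per week give an average interval of 7/2 = 3.5 days. Visits at least 48 hours apart within a five-day week, on the same two days each week, give gaps of 2, 3 or 4 days within the week and 5, 4 or 3 days across the weekend. Regrading the first or last severe visit therefore moves the duration by about 3 to 4 days on average (range 2 to 5), when the adjacent visit is also severe.
- Duration after radiotherapy: weekly visits, so about 7 days.
- A soup-dependent visit lying between other severe visits changes nothing, because duration runs from first onset to final resolution.
- An isolated late grade III that turns on soup moves duration by more than one interval, because the grade II days before it are then counted as severe.

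**The case against.** The strongest reply has four parts.

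**Soup is named once and explicitly as a soft solid.** An assessor who looks it up finds one answer, and beside eggs, pasta and fruit it can be read as soup with solid pieces. This stands for chunky soup. It does not help with smooth soup, where following the example means setting aside the definition printed with it. A reader might infer that all soup is a liquid under Section 11.1. The documents do not support that, because soup that needs chewing fails the no-chewing part of the liquid definition.

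**Safeguards exist.** Footnote 6 to the Schedule of Assessments provides for central scoring by the WHO criteria. Section 11.1 provides training, asks for as few assessors per patient as possible, and tells patients not to discuss their regimen with the assessor. A reader might infer that knowledge of the arm decides the grade. The documents do not show this, and these measures reduce the risk. However, none of them defines soup. The documents also do not say how diet information reaches the central assessor or is classified there. The training content and the assessment instrument are not in the documents, so they may already settle the point.

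**The affected group is narrow.** A patient who also manages eggs, pasta or soft fruit is grade II on either reading. This stands, and the documents do not say how many patients remain.

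**All analyses are exploratory.** This is true and limits the consequence. SOM remains the outcome on which the proof of concept is judged.

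**Conclusion.** The contradiction is real and should be corrected. Section 11.1 gives two answers for clear, smooth or pureed soup, and for a patient with ulcers whose most solid food is such soup those answers are grade II and grade III. The grade II side assumes that soft solid means a tolerated solid diet, which is natural but unwritten.

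The total effect on the trial cannot be computed. The 10-point shift in an arm's SOM incidence is an upper limit for one patient. The shift of about one visit interval in a patient's duration is the typical effect of regrading a single first or last severe visit.

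A reader might go further and say that one patient moves an arm's mean duration by 24/10 = 2.4 days, using the 24 days assumed in Section 13.1. That requires the whole episode to turn on soup, which nothing in the documents suggests. The planned comparison is also a Wilcoxon rank-sum test, not a comparison of means.

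**What to change.** In Section 11.1:

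- Under soft solids, replace soup with: *soup with solid pieces that need chewing, if the pieces are eaten*.
- Under liquids, add: *broth, smooth or pureed soup*.
- After the definitions, add: *A patient who tolerates a normal or modified soft solid diet is scored as tolerating solids (grade II if ulcers are present). Grade III requires ulcers and an intake of liquids only.*

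Use the same wording in assessor training, on the mucositis form and in the instructions to the central assessor. Moving all soup to liquids would be simpler, but it would create a new conflict for soup that needs chewing.

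The cost is a small protocol text amendment with its IRB submission and updated training material. No visits or additional measurements are needed. If patients are already enrolled, grades already recorded that turned on soup need a check so that scoring is consistent across the trial.

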 - A *brief* physical exam, to include ECOG status, by a Radiation Oncologist and/or Medical Oncologist and/or ENT or Head & Neck Surgeon must be done weekly during Pre-Treatment, Combination Treatment, and during the Mucositis Observation Follow-up until OM grade ≤ 1 is achieved.
6. Oral Mucositis Assessment will be performed by a trained on-site assessor at screening, day 1 prior to start of RRx-001 pretreatment, day 15 prior to the start of Combination Treatment (chemoradiation), twice a week (no less than 48 hours apart) during Combination Treatment (weeks 1 - 7), and once each week on the same day (± 1 day) during the Mucositis Observation Follow-up until an OM grade ≤ 1 is achieved. Lesions will be scored by a central assessor according to WHO ([Appendix C](#)) and WHO grade assessment will be communicated back to site study team by the central assessor.
7. Oral Mucositis Daily Questionnaire (OMDQ) to be completed in clinic at screening and then daily in the provided OMDQ Booklet starting Week 1 (protocol Day 15) of combination treatment, continuing through the Mucositis Observation Follow-up until an OM grade ≤ 1 is achieved. See [Appendix D](#).
8. Record current oral routines (i.e. smoking and chewing tobacco) at screening. If oral routines change, please update oral assessment accordingly. Review patient oral care instructions ([Appendix G](#)) and dispense oral hygiene kit following enrollment and prior to start of chemoradiation.
9. Lab Assessments include a Complete Blood Count (CBC) with differential, a Complete Metabolic Panel (CMP), magnesium and phosphate: to be performed at screening, weekly during Pre-Treatment, Combination Treatment, 28 Day Safety Visit, and as clinically indicated per institutional guidelines. CMP to include: sodium, potassium, glucose, calcium, albumin, bilirubin, ALT, AST, and Alk Phos.
10. Negative serum or urine pregnancy test required within 14 calendar days prior to start of treatment for women of childbearing potential.

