17. A 28 Day Safety Visit will occur 4 weeks (28 days) post last dose of radiation treatment (+5 day window). If the patient has an OM grade ≥ 2 , patient will continue with the Mucositis Observation Follow-up weekly visits until an OM grade of ≤ 1 is achieved. If the patient finished Combination Treatment with an OM grade ≤ 1 , the patient will return to clinic 28 days post IMRT (+ 5 days) for this 28 Day Safety Visit. Once the patient is assigned an OM grade ≤ 1 and has completed the 28 Day Safety Visit, the patient will proceed into Long Term Follow Up.
18. Long-Term Follow-Up may be performed via chart review. All procedures performed during the follow-up period should be recorded as Concomitant Procedures. Patients should continue to be followed monthly if experiencing an adverse event related to the investigational agent of RRx-001 until resolution, or event is assessed as a grade ≤ 2 .

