13.2 Efficacy Analysis

Statistical methods for the calculation and analysis of efficacy endpoints are provided below. Limited hypothesis-testing will be performed, as this is a small POC study. All statistical analyses are exploratory.

Duration of Severe Oral Mucositis (SOM): The duration of SOM (WHO grade 3 or 4) will be calculated as the number of days from the onset of SOM (first time a WHO grade 3 or 4 is observed) to the day when severe OM has resolved (first time WHO grade 2 or less is observed after last WHO grade 3 or 4). Durations of 0 will be assigned to patients who do not experience severe OM. Any patient who dies or withdraws prior to resolution of severe OM will be assumed to have severe OM for the remainder of the observation period. All available OM assessments will be used to derive efficacy endpoints, including WHO grades recorded during the treatment and follow-up period in order to capture resolution of OM.

The duration of SOM will be compared for each of the 3 RRx-001 regimens versus the untreated control group using the Wilcoxon rank-sum test. This rank-based test does not depend on normality assumptions for these small sample sizes. All patients randomized (the intent-to-treat population) will be used for this analysis.

Time to onset of SOM: The number of days from the start of chemotherapy until the date of first OM assessment grade 3 or 4 will be listed and summarized descriptively for each treatment group.

Incidence of SOM: The incidence of SOM (WHO grade 3 or 4) will be calculated as the number of patients with at least one OM WHO grade 3 or 4, divided by the number patients in the treatment group. Patients with no OM assessments will be assumed to have severe scores. Patients who die or withdraw without experiencing OM grade 3 or 4 will also be assumed to have severe scores. The incidence of SOM will be compared between each RRx-001 group and the control arm using Fisher's Exact test. Clopper-Pearson two-sided 95% confidence limits will be calculated for the proportion of patients with SOM in each treatment arm.

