Duration and incidence of ulcerative OM: The duration of ulcerative OM (WHO grade 2, 3, and 4) will be calculated in a manner similar to duration of severe OM. That is, the duration of ulcerative OM will be calculated as the number of days from the onset of ulcerative OM (first time a WHO grade 2, 3, or 4 is observed) to the day when ulcerative OM has resolved (first time WHO grade 0 or 1 is observed after last WHO grade 2, 3 or 4). A similar imputation scheme will be used in the event that patients die or withdraw prior to resolution of OM to grade 0 or 1. The Wilcoxon rank-sum tests will be used to compare treatment groups. Incidence of ulcerative OM will be calculated and analyzed as described above for severe OM.

Patient-reported pain: The average of patient-reported mouth and throat soreness (MTS) scores, graded on a scale from 0 (no soreness) to 4 (extreme soreness), will be summarized by treatment group during each study week and displayed graphically. The number of patients with scores of 0 or 1 will be enumerated by time and treatment group.

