Appendix D. Oral Mucositis Daily Questionnaire (OMDQ)

This questionnaire (see next page) has been used as a tool to assess oral mucositis in patients undergoing hematopoietic stem cell transplantation [[Stiff et al., 2006](#)].

Patients should be instructed to complete the OMDQ in its entirety in a comfortable area at about the same time each day. The OMDQ should be completed prior to the oral mucositis assessment on a given study day. For days the patient does not visit the clinic, the patient is to complete it at home.

Oral Mucositis Daily Questionnaire (OMDQ)

1. How would you rate your OVERALL HEALTH during the LAST 24 HOURS? (circle one number)

0	1	2	3	4	5	6	7	8	9	10
Worst possible			Halfway between worst possible and perfect health					Perfect health		

2. During the LAST 24 HOURS, how much MOUTH AND THROAT SORENESS did you have? (circle one number)

No soreness	0	→	If you circled 0, please skip to question 5
A little soreness	1		
Moderate soreness	2		
Quite a lot of soreness	3		
Extreme soreness	4		

3. During the LAST 24 HOURS, how much did MOUTH AND THROAT SORENESS limit you in each of the following activities? (circle one number)

	Not limited	Limited a little	Limited some	Limited a lot	Unable to do
A. Swallowing	0	1	2	3	4
B. Drinking	0	1	2	3	4
C. Eating	0	1	2	3	4
D. Talking	0	1	2	3	4
E. Sleeping	0	1	2	3	4

4. On a scale of 1 to 10, how would you rate your OVERALL MOUTH AND THROAT SORENESS during the LAST 24 HOURS? (circle one number)

0	1	2	3	4	5	6	7	8	9	10
No soreness			Halfway between worst possible and perfect health					Worst possible		

5. During the LAST 24 HOURS, how much DIARRHEA did you have? (circle one number)

No diarrhea	0	→	If you circled 0, STOP here
A little diarrhea	1		
Moderate diarrhea	2		
Quite a lot of diarrhea	3		
Severe diarrhea	4		

6. On a scale of 1 to 10, how would you rate your OVERALL DIARRHEA during the LAST 24 HOURS? (circle one number)

0	1	2	3	4	5	6	7	8	9	10
No diarrhea			Halfway between worst possible and perfect health					Worst possible diarrhea		

[figure not shown]

Study Day _____ Date: _____

Instructions: Please list all medications you have used or taken today.

Time	Medication Name	Dose per Unit	Number of Units	Reason for Using/Taking Medication
08:10 AM/PM	Tylenol Extra Strength Gel Capsules	500 mg	2 pills	Jaw Pain
03:15 AM/PM	Oral Anesthetic Paste Maximum Strength	Thin Layer	1 application	Inner Cheek irritation
: AM/PM				
: AM/PM				
: AM/PM				
: AM/PM				
: AM/PM				
: AM/PM				
: AM/PM				

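### Section 11.1 assigns patients who need feeding-tube assistance to the nothing-by-mouth category whatever they still eat; read literally, this can score a patient who takes food by mouth as WHO grade IV and so as severe oral mucositis (SOM)

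*Combined protocol and SAP*

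**What the plan says.** Section 11.1 bases the efficacy endpoints on WHO criteria and calls the definitions of solids, liquids and nothing by mouth critical. The nothing-by-mouth bullet covers patients who cannot "eat or swallow EXCEPT for medication". Its last sentence widens the category: "This would also be the best option for patients who require the assistance of a feeding tube".

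Appendix C does not mention tubes. Grade II is ulcers with solids tolerated, grade III is ulcers with intake restricted to liquids, and grade IV is "Oral alimentation impossible".

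Section 1.2, footnote 6, adds central grading: "Lesions will be scored by a central assessor according to WHO". It refers to the same Appendix C.

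In Section 13.2 one grade 3 or 4 reading makes a patient an SOM case. SOM duration ends at the "first time WHO grade 2 or less is observed after last WHO grade 3 or 4". Ulcerative mucositis (grades 2 to 4) ends at the "first time WHO grade 0 or 1 is observed after last WHO grade 2, 3 or 4". Under Section 1.2, footnote 17, while the grade is 2 or more the "patient will continue with the Mucositis Observation Follow-up weekly visits".

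**The concern.** The WHO grade depends partly on what the patient can take by mouth. The tube sentence replaces that observation with a different fact, whether the patient needs tube assistance. The two can differ, for example when a patient is moving on or off tube feeding and takes part of the diet orally.

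Section 3.1 expects some patients in this population to need tube feeding, so assessors will have to apply the sentence. Two assessors, one literal and one not, could grade the same patient II and IV. That difference spans the SOM threshold, on which SOM incidence, time to onset and duration all rest. A tube-only reading can raise a grade but cannot lower it.

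**Working it through.** The plan gives no figure on this point, and the sample size in Section 13.1 does not depend on it. The check is mainly a comparison of texts.

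**Step 1: from diet category to grade.** No section maps diet categories to grades. Of the Appendix C grades, only IV fits a patient classed as taking nothing by mouth. This link is inferred.

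**Step 2: what changes at a single reading in a tube-assisted patient.**

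| Actual state | Appendix C on actual intake | Literal tube rule | SOM status | Ulcerative status |
|---|---|---|---|---|
| No ulcers, still takes food by mouth | 0 or I | IV | no to yes | no to yes |
| Ulcers, eats solids | II | IV | no to yes | unchanged |
| Ulcers, liquids only | III | IV | unchanged | unchanged |
| Only medication by mouth | IV | IV | unchanged | unchanged |

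**Step 3: what changes in each endpoint.**
- *SOM incidence* changes only if the patient has no other grade 3 or 4 reading and is not already counted as severe by the imputation rules in Section 13.2.
- *Time to onset* changes only if a tube-only reading precedes the first true grade 3 or 4.
- *SOM duration* changes only if a tube-only reading starts an episode or carries it past its true end. A reading inside an existing episode adds no days.
- *Ulcerative mucositis and the weekly visits* change only at readings otherwise grade 0 or I.

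**Step 4: arithmetic per patient.** With 10 per arm (Section 13.1), one reclassified patient moves incidence by 1/10 = 10 percentage points. In weekly follow-up, one tube-only reading that extends an episode adds about 7 days for that patient, or 7/10 = 0.7 days to the arm mean. In general:

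shift in arm mean = patients × extending weekly readings × 7 / 10.

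The documents give no values for the first two terms. Assuming 1 to 2 patients with 1 to 4 such readings each:
- 1 × 1 × 7 / 10 = 0.7 days
- 1 × 4 × 7 / 10 = 2.8 days
- 2 × 1 × 7 / 10 = 1.4 days
- 2 × 4 × 7 / 10 = 5.6 days

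The planned difference is 24 − 6 = 18 days. The range of 0.7 to 5.6 days is only as good as the assumption.

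**Step 5: Fisher's exact test, 10 v 10, two-sided.** There are 17 tables with p < 0.05 and more SOM in the control arm.
- One extra case in the treated arm only: 6 of the 17 move to p ≥ 0.05 (for example 9/10 v 3/10, p = 0.020, becomes 9/10 v 4/10, p = 0.057); 11 stay significant.
- One extra case in each arm: possible in 11 tables, and 1 crosses (5/10 v 0/10, p = 0.0325, becomes 6/10 v 1/10, p = 0.0573).
- One extra case in the control arm only: 6 non-significant tables become significant (for example 8/10 v 3/10, p = 0.0698, becomes 9/10 v 3/10, p = 0.0198).

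These are counts of tables, not probabilities. Any one-patient misclassification at this sample size would do the same.

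**Step 6: could affected readings be found later?** Only in part. Item 3 of the daily questionnaire asks "how much did MOUTH AND THROAT SORENESS limit you in each of the following activities", including eating. It measures limitation from soreness, not intake or tube use, and is skipped when item 2 is 0. Concomitant procedures may show that a tube was placed, but not what the patient still ate.

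**The case against.** The strongest reply is that the sentence closes a bullet about patients who cannot eat, so it naturally means those who need a tube for that reason. It speaks of requiring a tube, not having one, and Exclusion Criterion 9 separates a requirement for tube nutrition from prophylactic placement. On that reading there is no conflict.

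Part of this stands. An unused prophylactic tube is not caught, and patients who require tube feeding at baseline are excluded. But Criterion 9 separates needing a tube from merely having one; it does not say that a patient who needs one eats nothing. Section 11.1 presents the tube group as an addition to those who cannot eat, and speaks of assistance, not sole nutrition. The narrower reading is plausible but unstated.

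A second reply is that the assessment instrument, the required training and central scoring may settle the matter in practice. They may, but the documents do not reproduce the instrument or the training content, and no section gives the central assessor a different diet rule.

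Third, the route to grade IV without ulcers owes something to Appendix C, whose grade IV text does not name ulcers. That stands: the tube sentence is not its only source.

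Fourth, reach is narrow. Section 3.1 describes liquid diets as common, and a tube-assisted patient with ulcers on liquids only is already grade III. That also stands.

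**Conclusion.** The wording conflict is real if the sentence is applied as written, and it bears on the endpoint threshold. It is a cheap improvement, of minor to should-fix weight. The conclusion rests on the literal reading and on the inferred step from nothing by mouth to grade IV. The firm size is 10 percentage points of arm incidence per reclassified patient; how many patients that would be is unknown.

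A reader might infer three stronger things that the documents do not support:
- *That the SOM comparison is biased for or against the drug.* Nothing shows that tube use in patients who still eat differs between arms, and Step 5 shows that the effect can go either way. All testing is exploratory.
- *That about a quarter of patients would be misgraded.* The figure in Section 3.1 describes feeding made necessary by mucositis and includes parenteral nutrition. It is not a rate of tube use in patients who still eat.
- *That ulcerative mucositis and follow-up are affected as widely as SOM.* A patient with ulcers who eats solids is already grade II, so neither changes.

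**What to change.** 1. Reconcile the tube sentence with Appendix C by limiting it to tube-fed patients who take nothing by mouth except medication, so that the diet component reflects actual oral intake. Do not simply delete it, because it is the only tube instruction in the diet definitions.
2. Record tube use and current oral intake at each mucositis assessment.
3. Add a sensitivity analysis of SOM incidence and duration that regrades tube-only grade IV readings on actual oral intake and ulcer status. Dropping those readings would leave gaps with no grade.
4. For readings already collected without these items, query grade IV on days when questionnaire item 2 is 0 or the eating line of item 3 shows little or no limitation. This is a partial check only.
5. Carry the wording into assessor training and central scoring.

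Minor: Section 11.1 lists soup as a soft solid but defines liquids as foods that take their container's shape. The two should be reconciled, since the choice falls on the grade II/III boundary.

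Cost: one clause, an addition to the assessment form, one sensitivity analysis and a short training update. Assessors must ask tube-assisted patients what they still take by mouth.
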